#### 10.1.4 Analysis of safety parameters

Safety parameters should be evaluated at each visit planned in this study, as well as at unscheduled visits.

Safety evaluation will be based on the following parameters (between Visits 1 and 3), compared between the investigational medicinal product and placebo:

Frequency of adverse events (AEs) and/or serious adverse events (SAEs) in the treatment groups, including:

1. Determination of the overall incidence in:
  - I. adverse events (AEs), regardless of their association to the treatment;
  - II. AEs related or possibly related to the medicinal product administration;
  - III. AEs requiring therapy discontinuation.

AEs recording will be based on spontaneous report by the patient, as well as on the results of a patient survey by a physician.

Adverse events will be encoded according to the last update of MedDRA terminology. They will be represented by a preferred term (PT) and a system organ class (SOC).

2. AEs incidence according to the results of the vital signs evaluation (HR, BP, BT, RR) at each visit vs placebo

Changes in the main vital signs over time and the frequency of pathological abnormalities revealed during physical examination will be summarized in groups, and a comparison will be made between groups using appropriate tests for quantitative and qualitative data (see below). Quantitative data will be compared using the t-test or the Mann-Whitney test, depending on the normality of the distribution (which will be evaluated using the Shapiro-Wilk test). Qualitative data will be compared using the Fisher's exact test or the chi-square test, depending on the number of prospective observations in one cell (<5 or ≥5).

3. AEs incidence according to the results of laboratory examinations on Days 7(± 2) and 15(± 2) and AEs incidence according to the ECG results 15(± 2) vs placebo;

Variations in the results of laboratory tests (carried out in the central laboratory) over time and the rate of pathological deviations from the norm of the study results (based on the central laboratory reference values), as well as the deviations rate of the ECG results at the Visit 3 will be summarized by groups, and comparison between groups shall be made using appropriate tests for quantitative and qualitative data (see paragraph 2).

4. AEs incidence according to the everyday patients' diaries records of well-being self-evaluation.

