The consideration of AAD studies for LGG from [16], concerning infections in adults (including *H. pylori*), gives 0.14 for a probiotic group and 0.22 for a control group.

Combining all the strains, we obtain an incidence of 0.26 for the placebo and 0.15 for the probiotic group.

The following indicators were used for calculations:

1. The difference of absolute risks of AAD in the placebo group and the treatment group is expected to be positive.

The incidence of AAD = 0.26 is assumed for the placebo and 0.15 for the treatment group.

Possibility of type I error: 0.05

Power of the study is 80%, which corresponds to the type II error: 0.20.

Statistical hypothesis is the evidence of superior efficacy:

$$H_0: OR = 1$$

$$H_1: OR \neq 1,$$

where OR is the odds ratio between both groups.

The ratio between the treatment and placebo group sizes is 1:1.

Amount of the patient in each group could be calculated using the following formula [2]:

$$n_T = n_R = \left(\frac{Z_{1-\alpha/2} + Z_\beta}{p_T - p_R} \right)^2 [p_T(1-p_T) + p_R(1-p_R)] = 208$$

Thus, the minimum number of patients required for statistical analysis is 416 (208 patients per group). Taking into account a 20% withdrawal rate, one needs to randomize 520 subjects (260 patients per group).

3. General analysis values

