3.1. Clinical and statistical significance

All the statistical tests within this study will be performed at 95% confidence level (threshold value p to confirm statistical significance is less than 0.05). The two-sided statistical criteria will be used for all other studied parameters.

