- A number of days of using symptomatic therapy to relieve symptoms of acute diarrhea in the treatment group as compared to the placebo group.

Due to the obvious difference between the distribution of these indicators from the normal (they have a discrete distribution), the nonparametric Mann–Whitney–Wilcoxon test implemented in the `wilcox.test` function will be used for intergroup comparison.

3. Other secondary endpoints:

- Weight change at Visit 3 compared with Visit 1 in the placebo group as compared to the treatment group. This BKT can have a distribution close to normal. Accordingly, at the first stage, the normality of the distribution will be assessed (using the Shapiro–Wilk test implemented in the shapiro.test function), at the second stage, either the t-test (t.test function) or the Mann–Whitney–Wilcoxon test (wilcox.test function) will be used.
- Stool consistency change (according to Bristol Stool Scale) (according to the diary) in the treatment group as compared to the placebo group; any individual changes in stool consistency will be classified as improved/unchanged/worsened, and the difference between the groups will be analyzed using chi-square criterion (chisq.test function).

8. Safety analysis

Safety parameters will be evaluated at every planned or unscheduled visit.

The safety assessment will be based on the following indicators (between Visits 1 and 3) compared between the investigational medicinal product and placebo:

- Changes in the vital signs over time and the incidence of pathological abnormalities revealed during the physical examination will be summarized by the group; a comparison will be made between the groups using appropriate tests for quantitative and qualitative data.

The data will be checked for compliance with the normal distribution law using the Shapiro–Wilk test.

Intergroup comparison of secondary endpoints related to quantitative scales will be performed using Student's t-test for independent samples if the data correspond to the normal distribution law; otherwise, the Mann–Whitney U test will be applied to independent samples.

Intergroup comparisons of secondary endpoints related to categorical scales will be performed using Pearson's chi-square test if the number of points in each cell of the crosstab is ≥ 5 , or Fisher's exact test if at least one of the crosstab cells contains < 5 points.

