The dynamics will be assessed using ANOVA methods with repeated measurements if the data correspond to the normal distribution, otherwise, the Friedman test will be applied.

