Appendix 1. Table layouts

Table No. 1. Example of a statistical table for a quantitative variable

Visit	Group	Parameter	Variable name
Visit number	Group 1	N	
		Missed	
		Mean	
		95% CI	
		SD	
		Median	
		Min	
		Max	
		Q1	
		Q3	
	IQR		
	Group 2	N	
		Missed	

STATISTICAL ANALYSIS PLAN

Visit	Group	Parameter	Variable name
		Mean	
		95% CI	
		SD	
		Median	
		Min	
		Max	
		Q1	
		Q3	
		IQR	

Table No. 2. Example of a group comparison table for a quantitative variable

Visit	No.	No.	No.	No.
Variable	variable name			

STATISTICAL ANALYSIS PLAN

Shapiro–Wilk test, p-value	Group 1				
	Group 2				
Student's t-test, p-value					
Mann–Whitney test, p-value					

Table No. 3. Example of a repeated comparison table for a quantitative variable

Variable	Group	Visit	Friedman test/ ANOVA for repeated measurements	Wilcoxon test/ Student's t-test for repeated measurements
variable name	Group 1	Comparison of visits		
		No. vs. No.		

STATISTICAL ANALYSIS PLAN

Variable	Group	Visit	Friedman test/ ANOVA for repeated measurements	Wilcoxon test/ Student's t-test for repeated measurements
		No. vs. No.		
		No. vs. No.		
		No. vs. No.		
		No. vs. No.		
		No. vs. No.		
	Group 2	Comparison of visits		
		No. vs. No.		
		No. vs. No.		
		No. vs. No.		
		No. vs. No.		

STATISTICAL ANALYSIS PLAN

Variable	Group	Visit	Friedman test/ ANOVA for repeated measurements	Wilcoxon test/ Student's t-test for repeated measurements
		No. vs. No.		
		No. vs. No.		

Table No. 4. Example of a statistical table for a categorical variable

Variable	Visit	Group	Variable value	Amount	% by group	% by groups for visit	Fisher's test, p-value
variable name	No.	Group 1	value				
			value				
		Group 2	value				
			value				

STATISTICAL ANALYSIS PLAN

Table No. 5. Example of a table of adverse events for calculating the number of all adverse events

Adverse events	Group	Amount	% of the number of AEs in the group	% of the total number of AEs	Binomial test, p-value
All adverse events	Group 1				
	Group 2				
SOC	Group 1				
	Group 2				
PT	Group 1				
	Group 2				

Table No. 6. Example of a table of adverse events for calculating the number of adverse events in the context

Adverse events	Group	variable name	Amount	% of the number of AEs in the group	% of the total number of AEs	Fisher's test, p-value
	Group 1	value				
		value				

STATISTICAL ANALYSIS PLAN

Adverse events	Group	Variable name	Amount	% of the number of AEs in the group	% of the total number of AEs	Fisher's test, p-value

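### Vital signs and laboratory values are compared without default adjustment for the Visit 1 value, by a test picked with Shapiro-Wilk, and the added within-arm visit tests say nothing about LRG-002 (minor)

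*SAP*

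**What the plan says.** **Between arms, vital signs.** SAP section 8 summarises changes over time by group and compares the groups. The sentence that names the method begins "Intergroup comparison of secondary endpoints related to quantitative scales will be performed using" and gives Student's t-test for independent samples if the data look normal by Shapiro-Wilk, otherwise Mann-Whitney. Protocol section 10.1.4, item 2, agrees: "Quantitative data will be compared using the t-test or the Mann-Whitney test, depending on the normality of the distribution". Item 3 of that section applies the same tests to laboratory results. Neither test takes a covariate.

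**Use of the Visit 1 value.** SAP section 5 and Protocol section 10.1.1 adjust for a baseline variable only in an additional analysis, and only when the arms differ significantly on it.

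**Over visits.** SAP section 8 continues: "The dynamics will be assessed using ANOVA methods with repeated measurements if the data correspond to the normal distribution, otherwise, the Friedman test". This sentence does not say whether the test is within or between arms. The shell for it, Table No. 3 ("Example of a repeated comparison table for a quantitative variable"), lists visit-against-visit comparisons under Group 1 and again under Group 2. There is no arm-by-visit term.

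**Body weight.** SAP section 7.2 analyses the change from Visit 1 to Visit 3 between arms: "at the first stage, the normality of the distribution will be assessed", and then a t-test or Mann-Whitney-Wilcoxon test is run. No within-arm test of weight is named. The protocol synopsis names only the Mann-Whitney-Wilcoxon test for continuous secondary parameters.

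**The concern.** Vital signs and laboratory values are measured at Visit 1 in every patient, so the strongest available predictor of the follow-up value costs nothing to use. A significant baseline difference is a poor trigger for using it. In a randomised trial such differences arise by chance, and the gain in precision depends on the correlation with follow-up, not on imbalance.

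Patients enter with active acute respiratory disease, and some improvement can be expected in both arms. A visit-against-visit test inside one arm picks up that improvement. If it comes out significant in one arm and not in the other, a reader of the report may take the contrast for a drug effect.

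The Shapiro-Wilk switch lets the reported method depend on features such as rounding. Table No. 2 sets out the normality test by group and by visit, and the SAP gives no rule for when these disagree. That shell also holds p-values only, with no estimate of the between-arm difference, which is what a safety reader most needs.

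**Working it through.** **1. The plan's own figure.** Inputs from SAP section 2.3: AAD rates 0.26 and 0.15, "Possibility of type I error: 0.05" (taken two-sided, as the formula uses Z at 1 − α/2), and "Power of the study is 80%, which corresponds to the type II error: 0.20".

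n = ((1.960 + 0.842)/0.11)² × [0.15 × 0.85 + 0.26 × 0.74] = 207.5, rounded up to 208 per arm. With 20% withdrawal, 208/0.8 = 260. Both figures reproduce. The documents give no SD, correlation or power for any vital sign, laboratory value or weight.

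**2. Precision.** Let r be the correlation between the Visit 1 and follow-up values (assumed), with equal SDs. In units of SD², the variance entering the arm contrast is:

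- follow-up value alone: 1
- change score: 2(1 − r)
- ANCOVA: 1 − r²

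ANCOVA relative to change is therefore (1 + r)/2, and relative to raw values 1 − r². The difference detectable with 80% power at n = 208 per arm is 2.802 × √(2 × variance/208), in SD units.

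| r (assumed) | ANCOVA / change | ANCOVA / raw | Detectable: raw | change | ANCOVA |
|---|---|---|---|---|---|
| 0.3 | 0.65 | 0.91 | 0.275 | 0.325 | 0.262 |
| 0.5 | 0.75 | 0.75 | 0.275 | 0.275 | 0.238 |
| 0.7 | 0.85 | 0.51 | 0.275 | 0.213 | 0.196 |

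For vital signs the applicable column is uncertain: the text of SAP section 8 speaks of changes, while Table No. 2 is arranged by visit. For weight the change column applies. At r = 0.98, a plausible value over two weeks, the ratio is (1 + 0.98)/2 = 0.99, a gain of about 1%.

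**3. Validity of the between-arm tests.** I simulated 2,000 trials per scenario with 208 per arm, normal data, r = 0.5, 0.7 and 0.9, a shift of 0.3 SD in both arms and no drug effect. The raw, change-score and ANCOVA tests rejected in 0.044 to 0.054 of trials. The Shapiro-Wilk two-stage test on follow-up values rejected in 0.044 to 0.053, and switched test in about 10% of trials.

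**4. Within-arm tests.** Suppose both arms shift by d SD and the drug does nothing. The SE of the mean change in one arm is √(2(1 − r)/208). At r = 0.5 this is 0.0693. With d = 0.3, d/SE = 4.33 and P(significant) = Φ(4.33 − 1.96) = 0.991; at r = 0.3 it is 0.955. With d = 0.1 and r = 0.5, P = 0.303, and the arms disagree with probability 2 × 0.303 × 0.697 = 0.42. At r = 0.3 and 0.7 the disagreement is 0.35 and 0.50.

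The number of tests is not small. Three scheduled visits give one overall and three pairwise p-values per arm, so 4 × 2 = 8 per variable and 8 × 5 = 40 for the five vital signs in the visit schedule (Protocol Table 6).

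**5. Shapiro-Wilk and rounding.** These are simulated arms of 208 with truly normal values, 600 per setting; all SDs are assumed.

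- Weight change, SD 0.8 to 1.2 kg, recorded to 0.1 kg: normality rejected in roughly 6 to 9% of arms. Recorded to 0.5 kg: 100%.
- Respiratory rate, a whole number per minute, SD 1.5 to 2: 100%.
- Whole-number values with SD 8 to 12: roughly 4 to 8%, so the effect is confined to coarsely recorded variables.

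**The case against.** The strongest reply is that nothing here is invalid. Both documents plan between-arm comparisons, these hold their type I error (step 3), and the within-arm tests are added to them. A reader might infer that the plan tests natural recovery in place of the drug. The documents do not support that.

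A reader might also say that the Visit 1 weight is ignored. It is not: weight is analysed as a change from Visit 1.

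Third, the large raw-visit loss (0.51 at r = 0.7) rests on a blank example shell. The text of SAP section 8 speaks of changes, for which the figure is 0.85. The within-arm reading of the visit tests also rests on a shell, but Table No. 3 is explicit in listing visits under each group.

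Fourth, the 100% rejection for weight needs recording to 0.5 kg. Protocol section 5.2.3.2.1 gives 0.5 kg as the permitted measurement error and states no recording unit. Rejection also only moves the analysis to Mann-Whitney, a valid test.

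Finally, patients with pyrexia above 38 °C are not enrolled, which limits how far temperature can fall, and no size of recovery is documented.

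All of this stands. It leaves three points: avoidable imprecision in the vital-sign and laboratory comparisons, within-arm p-values that carry no information about LRG-002, and a method that is not fixed in advance.

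**Conclusion.** The point holds as a minor one. For vital signs, and for laboratory values under the protocol, ANCOVA would cut the variance by 15 to 35% against change scores, or by 9 to 49% against raw visit values, for correlations between 0.3 and 0.7. Those correlations are assumptions, and which comparison the SAP intends is unclear. The within-arm tests would very probably be significant under a common shift of 0.3 SD, and would disagree between arms in 35 to 50% of trials under a common shift of 0.1 SD, with no drug effect in either case. These shifts are also assumed.

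For weight there is no precision argument and no within-arm test to remove. What remains is that the test depends on Shapiro-Wilk, and so may depend on recording resolution, and that the SAP and the protocol synopsis name different methods. A reader might infer that the Shapiro-Wilk step inflates false positives; under normal data it did not.

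The consequences are limited. Secondary efficacy is declared exploratory in both documents, safety also rests on adverse-event incidence, and the primary model, success criterion and sample size are untouched.

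**What to change.** - **SAP section 8:** for each vital sign and laboratory variable, prespecify one ANCOVA of the follow-up value (Visit 2, Visit 3) on treatment, Visit 1 value and age group. Report the adjusted between-arm difference with its 95% CI. This also settles whether raw values or changes are compared.
- **SAP sections 7.2 and 8:** remove the Shapiro-Wilk switch. For weight change, name one test and use it in both documents; the Mann-Whitney-Wilcoxon test already in the synopsis would need no protocol change.
- **SAP Appendix 1:** make Table No. 3 a descriptive table of changes by arm without p-values, and add the estimate and CI to Table No. 2.

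The cost is SAP wording and simpler code. No new data are needed and fewer tests are run. Because Protocol section 10.1.4 names the t-test and Mann-Whitney test, the change should be listed and justified as Protocol section 10.7 requires, before the final analysis starts.

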8.1. Adverse events

Safety assessment will also be based on the following parameters (between Visits 1 and 3) compared between the investigational medicinal product and placebo:

Incidence of adverse events (AEs) and/or serious adverse events (SAEs) in the treatment groups including:

- Overall AE rate as compared to placebo;
- AE rate according to the results of physical examinations during each visit compared with placebo;
- AE incidence according to the assessment of the vital signs (HR, BP, BT, RR) at each visit as compared to placebo;
- AE incidence according to the ECG results on Day 15 (± 2) in comparison with placebo;
- AE incidence according to the results of laboratory examinations on Days 7 (± 2) and 15 (± 2) as compared to placebo;
- AE incidence according to the results of daily self-examination of the state of health recorded in Self-Observation Diary.

The study doctor will review the entries in the Self-Observation Diary. If the study doctor believes that the information in the Diary complies with the AE criteria, they will ask the patient about this event and document all information about the AE (including the causality assessment).

The AEs will be described according to the scheme given below:

- AE description
- Severity of the adverse event (meeting the severity criteria)
- AE severity
- AE duration
- Relation to the IMP
- Measures taken in relation to the investigational medicinal product
- Measures taken in relation to the patient

- **Outcome**

Adverse events will be coded according to the MedDRA

Methods of descriptive statistics will be used to represent the results. A comparison of the incidence of new AE cases in the study groups will be performed using the Fisher's exact test or the chi-square test, depending on the number of proposed observations in one cell (< 5 or ≥ 5), and a comparison of the severity (and the possible causality between the administered medicinal product and AE) will be conducted using the Cochran–Armitage test for linear trends for ordered categorical data.

